7.2.1.3 Treatment-emergent adverse events related to study treatment

TEAEs related to study drugs are those TEAEs which have been reported as related to study treatment by the investigator, or for which this relationship is unknown (i.e., missing).

7.2.1.4 Treatment-emergent adverse events by intensity

AE intensity is reported by investigator using the following severity scale: mild, moderate, or severe.

For AEs with multiple intensities reported, the worst reported severity will be considered. If the intensity is missing, the AE will be considered as severe.

7.2.1.5 Non-treatment emergent adverse events

Non-treatment emergent AEs are those AEs with onset date/time \geq date/time of study drug administration +48 h, or \geq date of study treatment administration +2 days if the onset time is missing.

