7.2.1.2 Treatment-emergent adverse events

Treatment-emergent AEs (TEAEs) are those AEs with onset date/time \geq date/time of study drug administration and \leq 48 h after date/time of study treatment administration.

AEs for which time of onset is missing will still be counted as treatment emergent if onset date is \geq date of study drug administration and is \leq date of study treatment administration +2 days.

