7.2.1.6 Serious adverse events

A serious AE (SAE) is an AE that has been reported as serious by the investigator in the eCRF.

Treatment-emergent SAEs (TESAEs) are SAEs with onset date/time \geq date/time of study drug administration and \leq 48 h after date/time of study treatment administration.

Post study drug administration SAEs not qualifying as TESAEs, are non-treatment emergent SAEs.

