10 GENERAL DEFINITIONS AND DERIVATIONS

10.1 Analysis periods and visit windows

The on-treatment period is defined as the period starting from study drug administration up to 48th hour post administration. However, some assessments will not have the exact time, only the day. In this case it will be assumed that the 48 hours on-treatment period corresponds to the day of study drug administration and to the two following days (1st, 2nd and 3rd day of the on-treatment period).

This results in an over-estimated duration of the on-treatment period for those events that do not have assessment time.

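### SAP 7.2.1.5 includes the same cut-points as the TEAE definition, so an AE dated day +2 without an onset time (or at exactly 48 h) falls in both classes

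*SAP*

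**What the plan says.** SAP 7.2.1.2 defines a TEAE as an AE with onset from dosing up to and including "48 h after date/time of study treatment administration". It then adds a fallback: "AEs for which time of onset is missing will still be counted as treatment emergent if onset date is" on or after the dosing date and no later than "date of study treatment administration +2 days".

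SAP 7.2.1.5 defines a non-treatment-emergent AE as one with onset at or after "date/time of study drug administration +48 h, or" at or after "date of study treatment administration +2 days if the onset time is missing".

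Four other sections bear on the same boundary:

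- SAP 10.1 ends the on-treatment period at the 48th hour. For records with a date only, it counts the dosing day and the two days after it as on-treatment ("1st, 2nd and 3rd day of the on-treatment period"), and it acknowledges that this overstates the length of the period.
- SAP 2.3 starts safety follow-up at the 49th hour for timed records, and from the third day after administration for date-only records.
- SAP 7.2.1.6 defines the later class of SAEs as a remainder: "Post study drug administration SAEs not qualifying as TESAEs, are non-treatment emergent SAEs". SAP 7.2.1.9 does the same for AEs of special interest.
- SAP 7.2.2, Table 5, reports the two classes in separate columns as numbers of subjects. SAP 7.2.3 repeats the analyses as numbers of event occurrences for SAEs, treatment-related SAEs and non-serious AEs.

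**The concern.** Two classes that are reported side by side as different periods should not share members. Here both definitions include the cut-point, and for date-only records the cut-point is a whole calendar day. An event on that day satisfies both rules, and the SAP gives no order of precedence.

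If the two flags are programmed as written, the event appears in both columns of Table 5. If they are programmed as an if/else, it appears in one column, but which one depends on coding order that the SAP does not specify. In the occurrence counts of SAP 7.2.3, which are meant for disclosure to regulatory authorities, a single non-serious AE could be counted once in each period.

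**Working it through.** No sample size, power or alpha figure is involved, and the plan states no number to reproduce. The check is interval arithmetic on the two definitions. Let *t* be hours from dosing to onset for timed events, and *d* the onset date minus the dosing date in days for events with no onset time.

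| Class | Timed onset | Date-only onset | Source |
|---|---|---|---|
| TEAE | 0 ≤ t ≤ 48 | 0 ≤ d ≤ 2 | SAP 7.2.1.2 |
| Non-treatment-emergent | t ≥ 48 | d ≥ 2 | SAP 7.2.1.5 |
| On-treatment period | up to the 48th hour | d = 0, 1, 2 | SAP 10.1 |

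**Overlap as written.**
- Timed: {t ≤ 48} ∩ {t ≥ 48} = {48}, a single instant.
- Date-only: {0, 1, 2} ∩ {2, 3, …} = {2}, the whole of day +2.
- No post-dose onset falls outside both classes.

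Stepping through every minute over 31 days for three dosing times (08:00, 10:00, 14:30), and every day offset from 0 to 30, gives the same result.

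**Which section is out of line.** SAP 10.1 names d = 2 as on-treatment, in agreement with 7.2.1.2. For timed records, SAP 2.3 starts follow-up only at the 49th hour, so t = 48 also belongs to the treatment period. The third-day wording of 2.3 for date-only records is less explicit, so the day +2 allocation rests on 10.1. A date-only event on day +2 may in truth lie on either side of 48 h. With dosing at 10:00, 10 hours of that day fall before the 48 h mark and 24 − 10 = 14 hours after it. SAP 10.1 settles this by convention and says so.

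**Whether imputation removes the overlap.** SAP Appendix D imputes missing or incomplete dates. It has no rule for a complete date with a missing time, so it does not resolve the case, and it can create one. Take dosing on 30 March and an AE onset recorded only as April. The dosing date lies outside 1–30 April, so the lower limit, 1 April, is imputed. That is 30 March + 2 days with no time, and both definitions apply.

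**Which outputs are touched.**
- Treatment-emergent column of Table 5: 7.2.1.2 is unchanged, so no effect.
- SAE and AESI rows: the later class is the remainder, so there is no overlap. The administration-site row has no follow-up entry.
- Fatal AE row: 7.2.1.7 takes non-TEAEs with fatal outcome and post-dose onset, which reads most naturally as a remainder.
- General and related AE rows, follow-up column: affected.
- Occurrence counts in 7.2.3: SAEs are protected by 7.2.1.6, which leaves the non-serious AE counts.

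**After the fix.** With t > 48 and d > 2, both intersections are empty and every post-dose onset falls in exactly one class.

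**The case against.** The best defence is that the intended allocation is already in the SAP. Table 5 heads its columns as the treatment period and the safety follow-up period, and 10.1 assigns date-only day +2 records to the former. On that view 7.2.1.5 contains a drafting slip, not an open analysis choice. This stands as an argument about severity. It does not remove the contradiction, because 7.2.1.5 is the section that defines the class being tabulated.

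The defence also limits the consequences correctly. A reader might infer any of the following, and the documents support none of them:

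- *Events are double counted in general.* Only boundary records overlap.
- *The bleeding evaluation is compromised, because the boundary lies within the 3-day bleeding focus.* The haemorrhage row uses the remainder definition of 7.2.1.9 and cannot double count. The 3-day focus belongs to the Safety Event Committee (protocol 3.4), and nothing says that the committee uses the 7.2.1.5 classification. A bleed could overlap only within the general or related AE rows or, if non-serious, the occurrence counts.
- *The columns of Table 5 no longer add up to a post-dose total.* They count subjects, and a subject with events in both periods rightly appears in both. They need not add up even under correct definitions, and the table has no total column. Adding up matters only for the event counts of 7.2.3.
- *Date-only onsets are common on day +2.* After the 24 h visit, the next scheduled contact is the telephone call at 30–37 days (protocol Table 2), so missing clock times are plausible. No rate is given, and 7.2.1.2 treats a missing time as a fallback case.

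It is also fair to note that every AE summary listed in protocol 10.3.4.1 is treatment-emergent. The column at risk is a supplementary display added by the SAP.

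**Conclusion.** The overlap is real and follows directly from the text: exactly 48 h for timed onsets, and all of day +2 for onsets with no time. SAP 7.2.1.5 contradicts 7.2.1.2 and 10.1 on day +2, and 2.3 on timed onsets. As written, it places such events wrongly in the safety follow-up column of the general and related AE rows of Table 5. It also allows double counting of non-serious AE occurrences under 7.2.3.

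Severity is minor. The treatment-emergent results, the SAE and AESI rows and the primary PD analysis are unaffected. Every date-only AE on day +2 meets both definitions, but how many there will be cannot be derived from the documents. The conclusion assumes that the definitions are programmed as written. It rests on finding no tie-break rule in the SAP sections or in Appendix D.

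**What to change.** In SAP 7.2.1.5, replace *at or after* by *after* in both places: onset later than dosing + 48 h or, if the time is missing, onset date later than the dosing date + 2 days. Alternatively, define non-treatment-emergent AEs as post-dose AEs that do not qualify as TEAEs, which is the approach 7.2.1.6 and 7.2.1.9 already take for SAEs and AESIs. Either wording gives classes that are mutually exclusive and cover all post-dose AEs, and both agree with 10.1.

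The cost is two symbols or one sentence in the SAP, plus a check of the matching program line. Data collection, the TEAE definition and trial conduct do not change.

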7.2.1.6 Serious adverse events

A serious AE (SAE) is an AE that has been reported as serious by the investigator in the eCRF.

Treatment-emergent SAEs (TESAEs) are SAEs with onset date/time \geq date/time of study drug administration and \leq 48 h after date/time of study treatment administration.

Post study drug administration SAEs not qualifying as TESAEs, are non-treatment emergent SAEs.

7.2.1.7 Adverse events leading to death

An AE is considered as an AE leading to death if the AE outcome is fatal.

TEAEs leading to death are TEAEs with fatal outcome.

Non-TEAEs with fatal outcome and onset post-study drug administration are non-treatment emergent AEs leading to death.

7.2.1.8 Adverse events leading to study treatment discontinuation

Not applicable.

7.2.1.9 Other adverse events categories

Two AEs of special interest (AESIs) are defined, one will include any AE included in MedDRA SMQ “*Haemorrhage (excl. lab)*”, the other will include any AE included in the MedDRA high level group term (HLGT) “*Administration site reaction*”.

For each AESI, the events will be classified as treatment-emergent AESIs if event onset date/time \geq date/time of study drug administration and \leq 48 h after date/time of study treatment administration.

Similarly, each event not classified as treatment-emergent AESIs, and with onset being post-study treatment administration will be classified as non-treatment emergent AESIs.

7.2.2 Analysis

For all the AE variables described in Section 7.2.1, the incidence of subjects with the event will be summarized (frequency counts and percentages) by SOC and/or PT as describe in Table 5.

Table 5 Reporting of AEs categories by event onset

Adverse events	Onset during	
	Treatment period (treatment-emergent)	Safety follow-up period (non-treatment emergent)
Any AEs	SOC+PT, PT only	PT only
All AEs related to study treatment	SOC+PT, PT only	PT only
AEs related to study treatment	SOC+PT, PT only	PT only
AEs related to study treatment by intensity	SOC+PT	-
SAEs	SOC+PT, PT only	PT only
AEs leading to death	SOC+PT, PT only	PT only
AEs belonging to SMQ “ Haemorrhage (excl. lab) ”	PT only	PT only
AEs belonging to HLT “ Administration site reaction ”	PT only	-

-, not applicable; AE, adverse event; HLT, high level group term; PT, preferred term; SAE, serious adverse event; SMQ, Standardised MedDRA Query; SOC, system organ class.

For TEAEs by intensity, the incidence of subjects with events will be summarized (frequency counts and percentages) by maximum intensity (worst).

All AEs will be listed separately for subjects included in the SAF and for subjects not included in the SAF. SAEs will be flagged.

Specific listings will also be provided for SAEs and AESIs for the SAF only.

7.2.3 Analyses for key study data disclosure to regulatory authorities

The analyses described in Section 7.2.2 will also be performed on number of event occurrences, i.e., summarizing the total number of events, for SAEs, treatment-related SAEs, and non-serious AEs.

7.3 Death

Death is considered to have occurred if a primary cause of death is identified in the eCRF 'Death' form.

The original terms used by the investigators to describe deaths (i.e., death cause) are assigned PTs for classification and tabulation using the latest implemented MedDRA version dictionary.

Death will be classified as on study deaths (from study start to End-of-Study [EOS]) and on treatment deaths (within 2 days from study drug administration).

All deaths including cause of death will be listed, and flagged as per period of occurrence (baseline, on-study, and on-treatment periods).

7.4 Laboratory tests

7.4.1 Measurements

Only laboratory data received from the central laboratory [see protocol section 7.2.5.2] will be included in the analyses described in this section.

However, laboratory data received from local laboratories will be included in the listings.

Treatment-emergent laboratory abnormalities are central laboratory abnormalities for which blood sample collection were collected on the day of study drug administration or after, and up to the first 48 hours (2 days) after study administration, and that were not present at baseline.

Shift tables of on-treatment value vs baseline, for selected laboratory variables, may be provided according to results.

For each variable, the severity is based on the position of the value against reference ranges (central laboratory) and additional thresholds for significance [see [Appendix C](#)] and the worst abnormality is considered in each direction separately (lowest and highest).

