7.2.5 Laboratory assessments

7.2.5.1 Type of laboratory

A central laboratory (see central laboratory manual for contact details) will be used for all protocol-mandated laboratory tests, including re-tests due to laboratory abnormalities and laboratory tests performed at unscheduled visits.

Exceptional circumstances that may require recording of local laboratory results of the variables described in Section 7.2.5.2 (with corresponding normal ranges) include hospitalization of the subject due to a medical emergency, and missing central laboratory results from a scheduled or unscheduled visit.

If the 24 h post-dose central laboratory sample is lost or cannot be analyzed for whatever reason, the investigator may collect an additional sample for repeat analysis, as deemed medically needed, unless a local laboratory sample was collected within the same time-window and these test results are available.

Central laboratory reports will be sent to the investigator. In the event of specific (predefined) laboratory abnormalities, the central laboratory will alert sponsor personnel and the concerned site personnel. Alert flags that will trigger such notifications are displayed in the laboratory manual.

All laboratory reports must be reviewed, signed and dated by the investigator or delegate within 10 working days of receipt and filed with the source documentation. The investigator/delegate must indicate on the laboratory report whether abnormal values are considered clinically relevant or not. Clinically relevant laboratory findings that are known at the time of signing of informed consent must be recorded on the Medical History form of the CRF. Any clinically relevant laboratory abnormalities detected after signing of informed consent must be reported as an AE or SAE as appropriate [see Section 9], and must be followed until the value returns to within the normal range or is stable, or until the change is no longer clinically relevant.

Details about the collection, sampling, storage, shipment procedures, and reporting of results and abnormal findings can be found in the laboratory manual.

7.2.5.2 *Laboratory tests*

7.2.5.2.1 *Hematology*

- Hemoglobin (g/L)
- Hematocrit (L/L)
- Erythrocyte count (10^9 /L)
- Leukocyte count with differential counts (10^9 /L)
- Platelet count (10^9 /L)

7.2.5.2.2 *Clinical chemistry*

- Alanine aminotransferase (U/L)
- Aspartate aminotransferase (U/L)
- Alkaline phosphatase (U/L)
- Total and direct bilirubin (μ mol/L)

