10.2.3.2 Laboratory data

Laboratory analyses are based on data received from the central laboratory [see Section 7.2.5.2]. All transferred central laboratory data are taken into account regardless of whether they correspond to scheduled or unscheduled assessments.

Baseline laboratory test refers to the latest laboratory test performed prior to the first study treatment administration.

End-of-treatment laboratory test refers to the laboratory test performed on the day following the day of study treatment administration (Visit 3).

For each continuous laboratory parameter, the following variables will be summarized:

- Absolute value at each time point,
- Absolute change from baseline to each time point,
- Treatment-emergent marked laboratory abnormalities (i.e., up to 48 h after study treatment administration).

For categorical laboratory parameters, the following variables will be summarized:

- Proportion of subjects by categories at each time point.

Unless stated otherwise, no imputation for missing laboratory values will be performed.

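### A marked laboratory abnormality seen only in a local sample within 48 h of injection cannot enter the treatment-emergent count, because SAP 7.4.1 uses central results alone

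*SAP*

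**What the plan says.** **Source of the data.** SAP 7.4.1: "Only laboratory data received from the central laboratory [see protocol section 7.2.5.2] will be included in the analyses described in this section". The endpoint follows the same rule: "Treatment-emergent laboratory abnormalities are central laboratory abnormalities", sampled from the day of dosing up to 48 h and not present at baseline. Local values appear only in listings, flagged as not analysed (SAP 7.4.1 and 7.4.2). Protocol 10.2.3.2 has the same restriction ("Laboratory analyses are based on data received from the central laboratory"), so the SAP follows the protocol here.

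**When local results are recorded.** Protocol 7.2.5.1 provides for recording local results with their normal ranges in exceptional circumstances, which include "hospitalization of the subject due to a medical emergency, and missing central laboratory results from a scheduled or unscheduled visit".

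**The 24 h sample.** Protocol Table 2 schedules one post-dose laboratory test, at Visit 3; the Visit 2 test is pre-dose. If the 24 h central sample is lost or cannot be analysed, "the investigator may collect an additional sample for repeat analysis, as deemed medically needed", but not where the exception applies: "unless a local laboratory sample was collected within the same time-window and these test results are available". Footnote h of Table 2 repeats this.

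**Unscheduled central samples count.** Protocol 10.2.3.2: "All transferred central laboratory data are taken into account regardless of whether they correspond to scheduled or unscheduled assessments".

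**The endpoint.** Treatment-emergent marked laboratory abnormalities are a safety endpoint in protocol 6.3 and are tabulated as number and percentage of subjects under protocol 10.3.4.2.

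**The concern.** The protocol treats a same-window local result as sufficient reason not to repeat the central test, and the analysis then sets that result aside. With one scheduled post-dose test per subject, little else can fill the gap.

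The gap need not be random. Emergency hospitalisation is a named reason for local testing, so values held only locally may come disproportionately from subjects with an acute event. This is the first study of the drug in patients, and protocol 1.5.1 names bleeding as the main known risk of the class. A fall in haemoglobin is therefore a laboratory signal that the table should be able to show.

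The issue also reaches subjects who do have a central 24 h value. SAP 7.4.1 takes the worst abnormality in each direction, but among central values only. A fall found locally a few hours after injection and no longer present in the central 24 h sample would not be counted.

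**Working it through.** The documents state no laboratory abnormality rate and no expected number of subjects with local results only, so there is no figure to reproduce. The check follows the rules through and then illustrates the size.

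**Step 1: how each kind of subject is counted.** Two further rules matter. Protocol 10.2.3.2 plans no imputation of missing laboratory values. SAP 8.1.2 leaves missing values out of percentage denominators unless the table shells say otherwise. The shells are not in the documents, and SAP 7.4 does not name a denominator for this table.

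| Post-dose results within 48 h | Numerator | Denominator (SAP default) |
|---|---|---|
| Local only, abnormal | not counted | excluded as missing |
| Local abnormal, central 24 h normal | not counted | included, as having no abnormality |
| Local abnormal, central also abnormal (scheduled or unscheduled) | counted | included |

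In the first two rows the abnormality is absent from the numerator. Only the denominator differs.

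**Step 2: illustration.** Arm size N = 108 is from protocol 10.5. All other counts are assumptions: X = 10 subjects truly abnormal, k subjects with local results only, and a of those k abnormal.

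- All results counted: X/N = 10/108 = 9.3%.
- Central only, SAP default denominator: (X − a)/(N − k).
- Central only, all treated subjects as denominator: (X − a)/N.

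| k | a | SAP default | All treated |
|---|---|---|---|
| 1 | 1 | 9/107 = 8.4% | 9/108 = 8.3% |
| 3 | 0 | 10/105 = 9.5% | 10/108 = 9.3% |
| 3 | 1 | 9/105 = 8.6% | 9/108 = 8.3% |
| 3 | 3 | 7/105 = 6.7% | 7/108 = 6.5% |
| 5 | 0 | 10/103 = 9.7% | 10/108 = 9.3% |
| 5 | 5 | 5/103 = 4.9% | 5/108 = 4.6% |

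If local-only subjects are never abnormal, the default rule slightly overstates the rate. If they are abnormal more often than others, as emergency admission would suggest, it understates the rate.

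One subject in the second row of Step 1, with a normal central 24 h value, gives (10 − 1)/108 = 8.3% under either denominator.

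**Step 3: a rare event.** Take a single marked haemoglobin fall among the 2 × 108 = 216 active subjects, seen only locally in a subject with a normal central 24 h value. The count goes from 1/216 = 0.5% to 0/216. The exact one-sided 95% upper bound goes from 2.2% to 1.4%. The plan calculates no such bound; it is shown only for scale.

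**The case against.** Several points on the other side are sound.

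- **Central-only analysis is a prespecified and ordinary choice.** Protocol and SAP agree, and one laboratory avoids mixing assays. This stands for the descriptive statistics and the main table.
- **A clinical bleed would be seen elsewhere.** Clinically relevant laboratory abnormalities must be reported as AEs or SAEs, with no restriction to central results (protocol 7.2.5.1). Haemorrhage is an AE of special interest (SAP 7.2.1.9). The Safety Event Committee reviews unblinded data with a focus on major bleeding, and the local value is listed. This stands, but it does not restore the endpoint. AE reporting rests on the investigator's judgement of relevance, whereas the marked-abnormality count applies fixed thresholds. The haemorrhage query, by its title, leaves out laboratory terms.
- **Grading of local values cannot be fully checked.** The marked-abnormality thresholds in SAP Appendix C are redacted, so their fit to local results is unknown. This supports a supplementary count over a change to the main table.

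A reader might also infer more than the documents support:

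- *That subjects tested locally are scored as having no abnormality.* No text says so. With no central post-dose value, the default treats them as missing. They would count as not abnormal only if the unseen shells use all treated subjects. The inference is right only for a subject whose central value is normal.
- *That a local sample cancels the scheduled 24 h central draw.* It does not. The exception applies only once that sample is lost or cannot be analysed, and it removes only an optional repeat.
- *That a local sample taken around a bleed at 6 h would trigger the exception.* The only 24 h window that the documents give is ±2 h (protocol Table 3), and 6 h lies outside it. Such a value would be recorded under the emergency-hospitalisation provision instead.
- *That every locally tested subject is lost.* Anyone with a central value within 48 h, scheduled or unscheduled, is still analysed.

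**Conclusion.** The point holds in a limited form. An abnormality seen only in a local sample within 48 h of injection cannot enter the treatment-emergent laboratory table, although the protocol foresees such samples and has them recorded with normal ranges. The subject either drops out as missing (under the SAP default denominator) or, with a normal central 24 h value, is counted as having no abnormality.

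The size cannot be fixed from the documents. In the illustration, with 10 of 108 subjects abnormal, one abnormality missed among three local-only subjects moves the rate by 9.3 − 8.6 = 0.7 percentage points. For a rare event, one missed case can be the difference between one and none. Few subjects are likely to be affected. That the loss is informative is a reasonable inference from the named routes to local testing, but the documents do not establish it. The effect is confined to the laboratory abnormality counts, and the primary PD analysis is untouched.

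**What to change.** In SAP 7.4.1 and 7.4.2:

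1. Keep the descriptive statistics and the main treatment-emergent table on central data.
2. Add a supplementary count of treatment-emergent abnormalities that includes local values collected within 48 h after injection. Grade them against their recorded local ranges, and against the marked-abnormality thresholds where these can be applied. Flag them and show the result beside the central-only count.
3. State the denominator of the main table, for example subjects with at least one central post-dose value.
4. Report by arm how many subjects have only local, or no, post-dose results.

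Record the supplementary count in SAP 11.4 as an addition to the protocol analyses. The cost is a few sentences and the mapping of a small number of records that the CRF already holds. The drawback is some between-laboratory assay difference, confined to the supplementary count.
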